10.6 Electrocardiograms (ECG)

ECG parameters include heart rate (bpm), PR interval (ms), QRS duration (ms), QT interval (ms), and QT interval corrected by Fredericia's formula (QTcF) (ms). Any triplicate results collected on the ECG CRF will be averaged. ECGs will be interpreted by the Investigator as normal; abnormal, not clinically significant; or abnormal, clinically significant.

If QTcF interval results are not provided on the CRF, the interval will be calculated as:

$$\text{QTcF interval} = \text{QT/RR}^{0.33} \quad (\text{where RR} = 60 \div \text{heart rate})$$

The numbers and percentages of patients with maximum post-baseline QTcF interval values and maximum changes in QTcF interval values from baseline in the categories below will be summarized.

Absolute QTcF interval

- QTcF interval > 450 ms
- QTcF interval > 480 ms
- QTcF interval > 500 ms

Change from baseline in QTcF interval:

- QTcF interval increase from baseline > 30 ms
- QTcF interval increase from baseline > 60 ms

10.7 ECOG Performance Status

ECOG Performance Status results will be provided in a by-patient data listing.

10.8 Vital Signs

Vital signs collected include pulse rate (bpm), temperature (°C), systolic and diastolic blood pressure (mmHg), and pulse oximetry (%). Weight (kg) also was collected and will be presented with vital signs. A by-patient data listing will be provided.

10.9 Physical Examinations

Physical examination data will be provided in a by-patient data listing.

11 CHANGES TO THE PLANNED ANALYSIS

Additional details have been provided for analysis and data presentations described in the protocol, but no changes were made to the analyses specified in the protocol. Any deviations from the final approved sSAP will be described and justified in the sCSR.

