2.2 Secondary Objectives

The secondary objectives of this study are:

Dose Escalation:

- Evaluate the overall safety profile of HPN424 administered by intravenous (IV) infusion and subcutaneous (SC) injection
- Characterize single dose and multiple dose PK of HPN424
- Evaluate immunogenicity against HPN424
- Evaluate preliminary clinical anti-tumor activity
- Characterize the impact of HPN424 on activation of circulating lymphocytes and systemic soluble immune factors

Dose Expansion:

- Further characterize the safety and tolerability of HPN424 at the RP2D(s)
- Characterize single dose and multiple dose PK of HPN424 at the RP2D(s)
- Evaluate immunogenicity against HPN424
- Characterize the impact of HPN424 on activation of circulating lymphocytes and systemic soluble immune factors

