10 PLANNED STATISTICAL METHODS

10.1 General Considerations

Descriptive statistics will be used to summarize data including baseline patient characteristics, treatment with HPN424, safety variables and preliminary efficacy. Categorical or nominal variables will be summarized by frequency and percentage. Continuous variables will be summarized using standard summary statistics (n, mean, standard deviation, median, minimum, and maximum). Where appropriate, 95% confidence intervals around point estimates will be presented. Details of endpoints analyses will be described in the Statistical Analysis Plan.

No imputation of values for missing data will be performed except that missing or partial start and end dates for AEs and concomitant medication will be imputed according to prespecified, conservative imputation rules. Patients who withdraw or are lost to follow-up will be included in statistical analyses to the point of their last evaluation.

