10.7 Analysis of Safety

Safety summaries will include summaries in the form of tables and listings. For all patients, AE data will be listed by dose level cohort. The frequency (number and percentage) of treatment-emergent AEs will be summarized by system organ class and preferred term using the Medical Dictionary for Regulatory Activities (MedDRA). Summaries will also be presented by the severity of the AE and by relationship to study treatment. In addition, DLTs and all SAEs, including deaths, will be listed separately and summarized.

Laboratory shift tables containing counts and percentages based on NCI CTCAE (version 5.0) grade will be prepared by dose level cohort, laboratory parameter, and time. Summary tables will be prepared for each laboratory parameter. Figures of changes in laboratory parameters over time will be generated.

Changes in vital signs, ECGs, and ECOG scores will be tabulated and summarized.

Concomitant medications will be coded according to the World Health Organization (WHO) Drug Dictionary and listed.

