10.8 Analysis of Efficacy

Preliminary analysis of efficacy of HPN424 will be based on radiographic response per Prostate Cancer Working Group 3 (PCWG3) criteria (see the guidelines in [Appendix 6](#)).

Efficacy Endpoint Definitions:

- Objective Response Rate (ORR), defined as the proportion of patients who achieve a CR or PR determined by the investigator according to the PCWG3 criteria
- Progression-free Survival (PFS), defined as the time from first receipt of HPN424 to documented disease progression or death due to any cause, whichever occurs first (summarized descriptively using Kaplan Meier method)
- Duration of Response (DOR), defined as the time from the first observed response (CR or PR) to documented disease progression or death due to any cause (summarized descriptively using Kaplan Meier method)
- Overall Survival (OS), defined as the time from first receipt of HPN424 to death due to any cause (summarized descriptively using Kaplan Meier method)

Primary efficacy analyses will measure overall response rate. Secondary efficacy analyses will include PFS, DOR, and OS. Exploratory analyses will be summarized descriptively and relationships between clinical outcomes and safety may be explored.

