3 INTRODUCTION

The purpose of this synoptic statistical analysis plan (sSAP) is to reduce bias by prespecifying the intended analysis methodology, providing comprehensive and detailed documentation of the proposed analysis and reporting, and ensuring clear translations between the clinical objectives and statistical analysis methods.

This sSAP details the planned statistical analysis methods and data presentations for the synoptic clinical study report (sCSR) for the primary analyses for Study HPN424-1001, A Phase 1/2a Open-label, Multicenter, Dose Escalation and Dose Expansion Study of the Safety, Tolerability, and Pharmacokinetics of HPN424 in Patients with Advanced Prostate Cancer Refractory to Androgen Therapy. It was written in accordance with the International Conference on Harmonization of Technical Requirements for Registration of Pharmaceuticals for Human Use (ICH) guideline, E9: Statistical Principles for Clinical Trials ([ICH 1998](#)).

This sSAP should be read in conjunction with the study protocol, case report form (CRF), and any other applicable study documents. This sSAP is based on Protocol Amendment 7 Version 8.0 dated 24 September 2021 (UK Version 8.1 dated 01 December 2021, and CRFs from 15 November 2021. Protocol and sSAP revision history is as follows:

sSAP Version	Protocol Date	Protocol Version
V1.0, 03 March 2023	24 September 2021 01 December 2021 (UK only)	Amendment 7 Version 8.0 Amendment 7 Version 8.1

Analyses will be performed by Harpoon Therapeutics, Inc. using their Standard Operating Procedures.

The derivation and analysis of pharmacokinetic and biomarker endpoints will be discussed in a separate analysis plan.

On 10 March 2022, Harpoon Therapeutics decided to discontinue the study during Part 1 (dose escalation). Part 2 of the study was not initiated. The clinical study report will be a synoptic report focusing on safety data. This sSAP describes the original study objectives and study endpoints but will not summarize any efficacy data, which will only be reported in by-patient listings.

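### SAP section 11 says no protocol analyses were changed, but the SAP drops or reduces protocol-specified safety summaries and a Part 1 efficacy objective

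*SAP*

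**What the plan says.** SAP section 11 says that detail was added to the protocol's analyses but that "no changes were made to the analyses specified in the protocol". Its last sentence promises that deviations from the approved SAP will be explained in the study report; it does not deal with departures from the protocol.

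On safety, Protocol 10.7 says: "Changes in vital signs, ECGs, and ECOG scores will be tabulated and summarized". The same section asks for laboratory shift tables by dose level cohort, parameter and time, a summary table for every parameter, and figures of change over time. SAP 10.7 says: "ECOG Performance Status results will be provided in a by-patient data listing". SAP 10.8 gives vital signs the same treatment. SAP 10.5 plans only shifts from baseline grade to worst post-baseline grade, for CTCAE-graded parameters, by treatment group and overall. SAP 13.1 adds a table of patients with Grade 3 or higher values.

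On efficacy, Protocol 2.2 lists under Dose Escalation: "Evaluate preliminary clinical anti-tumor activity". Protocol 10.1 says: "Descriptive statistics will be used to summarize data including baseline patient characteristics, treatment with HPN424, safety variables and preliminary efficacy". Protocol 10.8 has PFS, DOR and OS "summarized descriptively using Kaplan Meier method". SAP 4.2 strikes the Dose Escalation objective, and SAP 3 says the plan "will not summarize any efficacy data, which will only be reported in by-patient listings".

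**The concern.** A changes section exists so that a reader can see where the analysis plan leaves the protocol and why. Here it tells the reader there is nothing to see. Someone relying on section 11 would take the safety tables to be the ones the protocol promised.

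Two things are at stake. First, the report is described as focused on safety, yet the undeclared reductions are all safety summaries. Vital signs are recorded before dosing, at 15, 30, 45 and 60 minutes, and at 4 hours for every IV dose (Protocol Appendices 1 and 2). That is 6 sets of readings per dose and, with 3 weekly doses, 18 per 21-day cycle per patient. A by-patient listing of that volume does not show group-level change. For the liver, Protocol 5.4.3 reports that most high-grade transaminase events followed the first dose or the first step-up, and the schedules add liver tests around the first three doses. A worst-grade shift discards that timing. C-reactive protein, which Protocol Appendix 8 treats as a useful though variable marker of CRS, has no CTCAE grade in SAP 13.3 and so appears in no table.

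Second, a stated Part 1 objective goes unanswered although the data are collected and the endpoints are defined in SAP 9.1.

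**Working it through.** The plan gives no figure to reproduce, so the check is a comparison of text. It is like for like: "This sSAP is based on Protocol Amendment 7 Version 8.0 dated 24 September 2021", which is the protocol supplied.

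- **Vital signs.** Protocol 10.7: changes tabulated and summarized. SAP 10.8 and 13.1: Listing 16.2.9.2 only. Dropped.
- **ECOG.** Protocol 10.7: changes tabulated and summarized. SAP 10.7 and 13.1: Listing 16.2.9.3 only. Dropped.
- **Laboratory, time dimension.** Protocol 10.7: shifts by time, and figures over time. SAP 10.5 and 13.1: worst post-baseline grade only (Tables 14.3.4.1 to 14.3.4.3), plus Table 14.3.4.4 for Grade 3 or higher. The time dimension is dropped.
- **Laboratory, coverage.** Protocol 10.7: a summary table for each parameter. SAP 10.5: graded parameters only. Reduced.
- **Laboratory, grouping.** Protocol 10.7: by dose level cohort. SAP 7.1: 12 fixed IV, 3 one-prime, 4 two-prime and 1 SC cohort (12 + 3 + 4 + 1 = 20) pooled into 4 groups. SAP 7.1 gives a reason, too many cohorts for one table, but does not describe this as a departure from the protocol.
- **ECG.** Protocol 10.7: changes summarized. SAP 10.6: QTcF categories, including change from baseline, in Table 14.3.5. Still summarized, so not counted here.
- **Efficacy.** Protocol 2.2 and 10.1: a Dose Escalation objective, with descriptive summary of preliminary efficacy. SAP 3, 4.2, 5.4 and 9: objective struck, Listings 16.2.6.1 to 16.2.6.8 only. Summary dropped.

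Tally of the table list in SAP 13.1: 6 under 14.1, 17 under 14.3.2, 1 at 14.3.3, 4 under 14.3.4, and 1 each at 14.3.5 and 14.3.6, so 6 + 17 + 1 + 4 + 1 + 1 = 30. Tables of vital signs: 0. ECOG: 0. Laboratory values by time: 0. Efficacy: 0. There is no list of figures.

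Is the stated reason enough? SAP 3 and 5.4 give the context: discontinuation on 10 March 2022 during Part 1, Part 2 not started, a synoptic report focused on safety. Not starting Part 2 explains the loss of the Dose Expansion endpoint. It does not explain striking an objective that belongs to Dose Escalation. SAP 9 may show how this arose: it assigns the efficacy endpoints to Part 2 while calling that part Dose Escalation, which is Part 1. A safety focus cannot by itself justify fewer safety summaries than the protocol specifies.

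**The case against.** The best defence is that the efficacy change is not hidden. SAP 3 and 5.4 state it with date and context, SAP 4 explains the strikethrough, and SAP 9 repeats that efficacy is listed only. That stands: for efficacy, the fault in disclosure is confined to section 11.

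The protocol's formal efficacy plan may also not reach Part 1. Protocol 10.3 limits the Efficacy Evaluable Population to patients treated at the assigned RP2D, and ORR is the Dose Expansion endpoint. That also stands, so Protocol 10.8 alone cannot be read as demanding ORR and Kaplan-Meier curves in escalation. The Part 1 objective in Protocol 2.2 and the general commitment in 10.1 remain, and they are enough to make listings without summaries a departure.

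CRS is well covered elsewhere. SAP 10.3 has a dedicated symptom module and ASTCT grading, which rests on fever, hypotension and hypoxia, and symptom tables are planned (14.3.2.16 and 14.3.2.17). It would therefore be wrong to say that the CRS signal is lost with the vital-sign summaries. Those tables show reported symptoms and grades, though, not measured change.

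A reader might infer selective reporting, because the SAP is dated 03 March 2023, almost a year after discontinuation, in an unblinded study. The documents do not support that. They do not show when the summaries were dropped or any motive beyond discontinuation; the cohort review committee was meant to see clinical activity throughout; and every patient's efficacy data will be listed.

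**Conclusion.** The point holds. The section 11 statement is inaccurate on two counts. Vital-sign and ECOG summaries are removed, and laboratory summaries reduced, without being identified as changes. The Part 1 anti-tumor objective is removed openly elsewhere in the SAP, but section 11 denies it. Laboratory reporting is reduced rather than abandoned, and ECG is still summarized.

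The size is a count of outputs: none of the 30 planned tables covers the four areas. No figure for lost precision on response can be given, because the documents do not state how many patients were treated; 130 is a planned ceiling.

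This is a matter of accurate declaration and complete reporting that should be corrected; it does not invalidate the remaining safety tables. It assumes that SAP 13.1 is the complete output list and that no separate document declares the changes. The UK protocol version named in SAP 3 was not available to check.

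**What to change.** 1. Rewrite SAP section 11 to list each dropped or reduced analysis with its reason: vital signs, ECOG, laboratory shifts by time, per-parameter laboratory summaries, laboratory figures, pooling of dose level cohorts, and efficacy summaries. Correct the label of the parts in SAP 9.
2. Restore the safety summaries by the four schedule groups in SAP 7.1: worst change from baseline in vital signs, an ECOG shift table, and laboratory summaries over time, at least for key parameters such as ALT, AST and bilirubin. Justify in section 11 any parameter still omitted.
3. Add one descriptive Part 1 efficacy table by the same groups: response with exact 95% CI, best PSA change, and Kaplan-Meier PFS and OS. State the denominator, since the Safety Population is the only set in SAP 6.3. Show confirmed and unconfirmed response separately: SAP 9.1.1 requires no confirmation for BOR, whereas Table 21 in Protocol Appendix 6 requires soft-tissue response to be confirmed at least 9 weeks later. Label the table descriptive, because three of the four groups pool several dose levels.

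Most inputs already feed Listings 16.2.6.1, 16.2.6.8, 16.2.8.2, 16.2.9.2 and 16.2.9.3; confirmed response may need one further derivation. The cost is a small amount of extra programming and a slightly longer synoptic report.

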13 APPENDICES

13.1 List of Planned Tables and Listings

All tables and listings will be numbered according to ICH E3 Guidelines.

Tables:

14.1 = demographic data

14.3 = safety data, with:

14.3.1 = adverse events

14.3.2 = listings of deaths, other serious and significant adverse events

14.3.3 = narratives of deaths, other serious and significant adverse events

14.3.4 = abnormal laboratory values

14.3.6 = study drug exposure

Listings:

16.2.1 = discontinued patients

16.2.2 = protocol deviations

16.2.4 = demographic data

16.2.5 = compliance and/or drug concentration data

16.2.6 = individual efficacy response data

16.2.7 = adverse events

16.2.8 = individual laboratory measurements

Table of Contents – Tables

Table Number	Description
14.1.1	Patient Enrollment
14.1.2	Patient Disposition
14.1.3	Protocol Deviations
14.1.4	Demographics
14.1.5	Baseline Disease Characteristics
14.1.6	Prior Cancer Therapy
14.3.2.1	Overall Summary of Treatment Emergent Adverse Events
14.3.2.2	Summary of Treatment Emergent Adverse Events by System Organ Class and Preferred Term
14.3.2.3	Summary of Treatment Emergent Adverse Events by Preferred Term
14.3.2.4	Summary of Treatment Emergent Adverse Events Related to HPN424 by System Organ Class and Preferred Term
14.3.2.5	Summary of NCI CTCAE Grade 3 or Higher Treatment Emergent Adverse Events by System Organ Class and Preferred Term
14.3.2.6	Summary of NCI CTCAE Grade 3 or Higher Treatment Emergent Adverse Events Related to HPN424 by System Organ Class and Preferred Term
14.3.2.7	Summary of Serious Treatment Emergent Adverse Events by System Organ Class and Preferred Term
14.3.2.8	Summary of Serious Treatment Emergent Adverse Events Related to HPN424 by System Organ Class and Preferred Term
14.3.2.9	Summary of Treatment Emergent Adverse Events with an Outcome of Death by System Organ Class and Preferred Term
14.3.2.10	Summary of Treatment Emergent Adverse Events Related to HPN424 with an Outcome of Death by System Organ Class and Preferred Term
14.3.2.11	Summary of Treatment Emergent Adverse Events That Lead to Discontinuation of HPN424 by System Organ Class and Preferred Term
14.3.2.12	Summary of Treatment Emergent Adverse Events Related to HPN424 That Lead to Discontinuation of HPN424 by System Organ Class and Preferred Term
14.3.2.13	Summary of Treatment Emergent Adverse Events That Lead to HPN424 Dose Modifications by System Organ Class and Preferred Term
14.3.2.14	Summary of Treatment Emergent Adverse Events Related to HPN424 That Lead to HPN424 Dose Modifications by System Organ Class and Preferred Term
14.3.2.15	Summary of Dose Limiting Toxicity (DLT) Adverse Events by System Organ Class and Preferred Term
14.3.2.16	Summary of CRS Signs and Symptoms by Preferred Term (From CRS Symptom CRF)
14.3.2.17	Summary of IRR Signs and Symptoms by Preferred Term (From CRS Symptom CRF)

Table Number	Description
14.3.3	Summary of Deaths
14.3.4.1	Safety Laboratory Assessment Shift Table – Serum Chemistry Change from Baseline to Maximum Post-Baseline NCI CTCAE Grade
14.3.4.2	Safety Laboratory Assessment Shift Table – Hematology Change from Baseline to Maximum Post-Baseline NCI CTCAE Grade
14.3.4.3	Safety Laboratory Assessment Shift Table – Coagulation Change from Baseline to Maximum Post-Baseline NCI CTCAE Grade
14.3.4.4	Safety Laboratory Assessment Summary of Patients with Post-Baseline NCI CTCAE Grade 3 or Higher
14.3.5	Summary of 12-Lead Electrocardiogram Abnormalities and Potential QTcF Interval Prolongation
14.3.6	Study Drug Exposure and Compliance

Table of Contents - Listings

Listing Number	Description
16.2.1	Patient Disposition
16.2.2	Patient Enrollment and Eligibility (Inclusion / Exclusion)
16.2.3	Protocol Deviations
16.2.4.1	Demographics
16.2.4.2	Prostate Cancer Medical History
16.2.4.3	Prior Anticancer Therapy
16.2.4.4	Prior Radiation Therapy
16.2.4.5	Prior Prostate Cancer-related Surgery
16.2.4.6	Medical History
16.2.5.1	HPN424 Administration
16.2.5.2	HPN424 Infusion Interruptions
16.2.5.3	Hospital Admission
16.2.6.1	Overall Efficacy Endpoints
16.2.6.2	Radiographic Scans
16.2.6.3	Target Lesions
16.2.6.4	Non-target Lesions
16.2.6.5	New Lesions
16.2.6.6	Bone Scan Assessment
16.2.6.7	Overall Disease Assessment

Listing Number	Description
16.2.6.8	PSA Results
16.2.7.1	Adverse Events
16.2.7.2	Serious Adverse Events
16.2.7.3	Dose-limiting Toxicities
16.2.7.4	Adverse Events Leading to Treatment Discontinuation
16.2.7.5	Adverse Events Leading to HPN424 Dose Modifications
16.2.7.6	Fatal Adverse Events
16.2.7.7	Cytokine Release Syndrome / Infusion Related Reactions Symptoms
16.2.7.8	Deaths
16.2.8.1	Laboratory Results: Hematology
16.2.8.2	Laboratory Results: Chemistry and Testosterone
16.2.8.3	Laboratory Results: Coagulation
16.2.8.4	Laboratory Results: Urinalysis
16.2.8.5	NCI CTCAE Grade 3 or Higher Laboratory Results
16.2.8.6	Patients who had laboratory values that Meet Criteria for Hy's Law
16.2.8.7	Central Laboratory Sample Collection
16.2.8.8	Serum Cytokines – Local Lab
16.2.9.1	12-Lead ECG
16.2.9.2	Vital Signs
16.2.9.3	ECOG Performance Status
16.2.9.4	Physical Examination
16.2.10.1	Prior and Concomitant Medications and Pre-meds
16.2.10.2	Concomitant Procedures
16.2.11.1	Safety Follow-Up
16.2.11.2	Survival Status / Long Term Follow-Up Status

13.2 Progression-free Survival Censoring Rules

(Censor for new anti-cancer therapy but not for treatment withdrawals.)

Situation	Date of Progression or Censoring	Outcome
Death before first assessment visit	Date of death	Progressed
No Baseline tumor assessments	Day 1	Censored
Death or progression after more than one missed assessment before switch to other anti-cancer therapy	Date of last radiological assessment of measured lesions	Censored
Progression documented before switch to other anti-cancer therapy	Earliest of the following assessed before switch to other anti-cancer therapy: 
• Date of radiological assessment showing new lesion (if progression is based on new lesion); or• Date of last radiological assessment of measured lesions (if progression is based on increase in sum of measured lesions)	Progressed
Death between adequate assessment visits before switch to other anti-cancer therapy	Date of death	Progressed
Switch to other anti-cancer therapy.	Date of last radiological assessment of measured lesions prior other anti-cancer therapy	Censored
No progression before switch to other anti-cancer therapy	Date of last radiological assessment of measured lesions	Censored

Source: Clinical Trial Endpoints for the Approval of Non-Small Cell Lung Cancer Drugs and Biologics, Appendices C and D

13.3 Safety Laboratory Reporting Specifications

Laboratory Test Full Name	Abbreviation	Reported Units (SI)	Sort Order [1]	CTCAE v5.0 Grading [2]	Decimal places	Textbook Normals / Source [3]
Hematology						
Hemoglobin	Hgb	g/L	1	Dec [1,2,3] / Inc [1,2,3] [4]	0 (XXX)	120 – 160 (female) 140 – 170 (male)
Hematocrit	Hct	L/L	2	-	2 (0.xx)	0.36 – 0.47 (female) 0.41 – 0.51 (male)
Red Blood Cell Count (Erythrocytes)	RBC	10 ¹² /L	3	-	1 (X.x)	4.2 – 5.9
Platelet Count	Plt	10 ⁹ /L	4	Dec	0 (XXX)	150 - 350
White Blood Cell Count (Leukocytes)	WBC	10 ⁹ /L	5	Dec / Inc [3]	1 (XX.x)	3.9 – 10.7
Neutrophils	ANC	10 ⁹ /L	5.1	Dec	1 (XX.x)	1.8 – 8.5 (from JAMA)
Lymphocytes	Lymph (abs)	10 ⁹ /L	5.2	Dec / Inc [2,3]	1 (XX.x)	1.0 – 4.8 (from JAMA)
Monocytes	Mono (abs)	10 ⁹ /L	5.3	-	1 (XX.x)	0.0 – 0.8 (from JAMA)
Eosinophils	Eos (abs)	10 ⁹ /L	5.4	Inc [1]	1 (XX.x)	0.0 – 0.45 (from JAMA)
Basophils	Baso (abs)	10 ⁹ /L	5.5	-	1 (XX.x)	0.0 – 0.2 (from JAMA)
Neutrophils	Neut (%)	%	N/A*	-	1 (XX.x)	20 – 59 (from JAMA)
Lymphocytes	Lymph (%)	%	N/A*	-	1 (XX.x)	10 – 34 (from JAMA)
Monocytes	Mono (%)	%	N/A*	-	1 (XX.x)	2 – 4 (from JAMA)
Eosinophils	Eos (%)	%	N/A*	Inc [1]	1 (XX.x)	0 – 2.7 (from JAMA)
Basophils	Baso (%)	%	N/A*	-	1 (XX.x)	0 – 0.3 (from JAMA)
Chemistry – Electrolytes						
Carbon Dioxide	CO2	mmol/L	1	-	0 (XX)	23 – 28
Calcium	Calc	mmol/L	2	-	1 (X.x)	2.2 – 2.6
Corrected calcium (serum calcium) [5]	CalcCor	mmol/L	3	Dec / Inc	1 (X.x)	2.2 – 2.6

Laboratory Test Full Name	Abbreviation	Reported Units (SI)	Sort Order [1]	CTCAE v5.0 Grading [2]	Decimal places	Textbook Normals / Source [3]
Chloride	Chlor	mmol/L	4	-	0 (XXX)	98 – 106
Magnesium	Magnes	mmol/L	5	Dec / Inc [1,3,4]	2 (X.xx)	0.62 – 0.99
Phosphorus	Phos	mmol/L	6	-	2 (X.xx)	0.97 – 1.45
Potassium	Pot	mmol/L	7	Dec [1,3,4] / Inc	1 (X.x)	3.5 – 5.0
Sodium	Sod	mmol/L	8	Dec [1,3,4] / Inc	0 (XXX)	136 – 145
Chemistry – Hepatic						
Total Protein	TProt	g/L	1	-	0 (XX)	60 - 78
Albumin	Alb	g/L	2	Dec [1,2,3]	0 (XX)	35 – 55
Globulin	Glob	g/L	3	-	1 (XX.x)	25 – 35
Alkaline Phosphatase	ALP	U/L	4	Inc	1 (X.x)	36 – 92
Bilirubin Total	TBili	umol/L	5	Inc	1 (XX.x)	5.1 – 20.5
Bilirubin Direct	DBili	umol/L	6	-	1 (XX.x)	0.0 – 5.1
Alanine Aminotransferase	ALT	U/L	7	Inc	2 (X.xx)	0 – 35
Aspartate Aminotransferase	AST	U/L	8	Inc	2 (X.xx)	0 – 35
Chemistry – Renal						
Blood Urea Nitrogen [6]	BUN	mmol/L	1	-	1 (X.x)	2.9 – 7.1
Urea [6]	Urea	mmol/L	2	-	1 (XX.x)	2.9 – 9.4
Creatinine	Creat	umol/L	3	Inc	0 (XXX)	61.9 – 115
Chemistry – Other						
Glucose [7]	Gluc	mmol/L	1	Dec	1 (XX.x)	3.9 – 5.8 (fasting)
Lactate Dehydrogenase	LDH	U/L	2	Inc	2 (X.xx)	60 – 160
Amylase	Amylase	U/L	3	Inc	2 (X.xx)	0 – 130

Laboratory Test Full Name	Abbreviation	Reported Units (SI)	Sort Order [1]	CTCAE v5.0 Grading [2]	Decimal places	Textbook Normals / Source [3]
Lipase	Lipase	U/L	4	Inc	2 (X.xx)	0 – 95
Uric Acid	Uric	umol/L	5	-	0 (XXX)	150 – 470
Alkaline Phosphatase, Bone Specific	BAP	mcg/L	6	-	1 (XXX.x)	0 – 20 (Mayo Clinic web site)
C-Reactive Protein	CRP	nmol/L	7	-	1 (XXX.x)	< 100 (Mayo Clinic web site)
Testosterone	TST	ng/dL	8	-	1 (XXXX.x)	300 - 1200
Coagulation						
International Normalized Ratio [8]	INR	ratio	1	Inc [1,2,3]	1 (X.x)	0.8 – 1.2 (healthy normals from Mayo Clinic web site)
Activated Partial Thromboplastin Time	aPTT	s	2	Inc [1,2,3]	0 (XX)	25 – 35
Prothrombin Time	PT	s	3		0 (XX)	11 – 13

All tables and listings must include the footnote: *See Statistical Analysis Plan Sections 13.3 and 13.4 for details regarding laboratory grading*

[1] Sort order (within panel) – N/A* are results that may be derived for analysis purposes and are reported only in listings (not tables).

[2] All CTCAE grading is based exclusively on quantitative laboratory results alone. Any associated clinical assessment by the investigator should be reported as an adverse event. When the CTCAE grade overlaps ranges based on clinical assessment, the higher grade is assigned.

[1,2,3,4] Indicates that not all grades are assigned in CTCAE – only those indicated are assigned by laboratory quantitative results

[3] Textbook normals to be used in absence of local normal ranges where reported units are obvious. Source is Merck Manual 2015 unless otherwise described

[4] For hemoglobin grading, in order to maintain the intention of CTCAE v4.03, the assumption is made that grading for increased levels are compared to ULN if baseline result is within normal range, or above baseline if baseline is above ULN.

[5] Serum calcium is corrected for albumin to assign CTCAE Grade; corrected calcium is derived as follows:

$$\text{corrected-CA (mmol/L)} = \text{serum-CA (mmol/L)} + 0.020 * (40 - \text{albumin (g/L)})$$

[6] To convert a BUN result in mg/dL to a Urea result in mmol/L, multiply the BUN result by 0.357. To convert a Urea result in mmol/L to a Urea result in mg/dL, multiply the mmol/L result by 6.

[7] Glucose results are assumed to be fasting for assignment of normal ranges and CTCAE grading.

[8] International Normalized Ratio assumes subjects are not on anticoagulant therapy.

